17.2. SECONDARY SAFETY ENDPOINTS

17.2.1. ADVERSE EVENTS

Adverse Events (AEs) related to the IC or SK procedure only will be collected from the start of intervention until the last follow-up visit at the time points specified in the schedule of activities (Section 3.2).

All Serious Adverse Events (SAEs) related to the IC or SK procedure only will be collected from the start of intervention until the last follow-up visit at the time points specified in the schedule of activities (Section 3.2). However, any SAEs assessed as related to study participation (e.g., study intervention, protocol-mandated procedures, invasive tests) will be recorded from the time a participant consents to participate in the study.

AEs and SAEs will be presented on the ICSK population and coded using MedDRA version 23.0 or above.

An overall summary table of number of participants within each of the categories described below, will be provided by method of tissue collection (impression cytology/superficial keratectomy) summarizing:

- Participants with at least one AE related to the IC or SK procedure.
- Participants with at least one SAE related to the study participation or to the IC or SK procedure.
- Participants with at least one SAE leading to study discontinuation
- Participants with AE leading to death.

AEs and SAEs will be presented in tables by PT and sorted by decreasing frequencies on total, and broken down by maximum grade. AEs will be graded according to the NCI Common Terminology Criteria of Adverse Events (NCI CTCAE) Version 5.0.

Participants will be counted only once for each PT even if they have multiple records of the same PT. If a participant reports an AE more than once within that PT, the AE with the worst-case grade will be used in the corresponding grade summaries.

Document: \\ieedc-vnasc01\Biosdata\GSKGSK2857916\UZA78766\Biostatistics\Documentation\SAP\UZA78766_214098_SAP_v2.0_12OCT2022.docx

Author: PPD Version Number: 2.0
Version Date: 12OCT2022

Template No.: CS_TP_BS016 Revision 6

Reference: CS_WI_BS005

Effective Date: 02Dec2019

AEs leading to Death are those events which are recorded on the Adverse Events page of the parent study eCRF as at least one of the following criteria:

- AE Term: "Death"
- Outcome: "Death related to adverse event"
- Seriousness: Results in death
- Toxicity grade (CTCAE): Grade 5

[figure not shown]
AEs leading to death will be presented in a by-participant listing on the all-treated population.

All secondary safety data will also be included in a by-participant listing on the all-treated population.

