7. DISCONTINUATION OF STUDY INTERVENTION AND PARTICIPANT DISCONTINUATION/ WITHDRAWAL

7.1. Participant Discontinuation/Withdrawal from the Study

- A participant may withdraw from the study at any time at his/her own request or may be withdrawn at any time at the discretion of the investigator for safety, behavioral, or compliance reasons. This is expected to be uncommon.
- At the time of discontinuing from the study, if possible, an early discontinuation visit should be conducted, as shown in the SoA (Section 1.3). See SoA for data to be collected at the time of study discontinuation and follow-up and for any further evaluations that need to be completed.
- The participant will be permanently discontinued both from the study intervention and from the study at that time.
- If the participant withdraws consent for disclosure of future information, the sponsor may retain and continue to use any data collected before such a withdrawal of consent.
- If a participant withdraws from the study, he/she may request destruction of any samples taken and not tested, and the investigator must document this in the site study records.

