8.1.3. Time Period and Frequency for Collecting AE and SAE Information

- All SAEs related to the IC or SK procedure only will be collected from the start of intervention until the last follow-up visit at the time points specified in the SoA. However, any SAEs assessed as related to study participation (e.g., study intervention, protocol-mandated procedures, invasive tests) will be recorded from the time a participant consents to participate in the study.
- AEs related to the IC or SK procedure only will be collected from the start of intervention until the last follow-up visit at the time points specified in the SoA (Section [1.3](#)).
- Medical occurrences that begin before the start of study intervention but after obtaining informed consent will not be collected.
- SAEs related to the IC and SK procedure will be recorded and reported to the sponsor or designee immediately, and under no circumstance should this exceed 24 hours, as indicated in [Appendix 2](#) . The investigator will submit any updated SAE data to the sponsor within 24 hours of it being available.
- Investigators are not obligated to actively seek information on AEs or SAEs after the conclusion of study participation. However, if the investigator learns of any SAE, including a death, at any time after a participant has been discharged from the study, and he/she considers the event to be reasonably related to the study intervention or study participation, the investigator must promptly notify the sponsor.

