9.3. Analysis Methods

No formal statistical tests of hypothesis will be performed. All participants who have SK in this program will be included in the safety analysis.

Demographic characteristics and dosing level and duration will be summarized using descriptive statistics (i.e., categorical variables will be described by absolute and relative frequencies), while continuous variables will be summarized by mean, standard deviation, quartiles, minimum, and maximum. The available information on all nonserious AEs leading to discontinuation, SAEs, and all other AEs (including AEs of special interest) will also be summarized using descriptive statistics.

All available demographic and safety data will be included in the data listings and tabulations. No imputation of values for missing data will be performed. Participants who

are lost to follow-up will be included in the statistical analysis to the point of their last examination. All data will be examined using standard data management operating procedures.

Changes in corneal epithelial findings from pre to post procedure, pathological and ^{CCI} [REDACTED] results in safety population will be tabulated in a descriptive manner.

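### The only discontinuation row in the SAP's AE overview counts SAEs alone, although Protocol 9.3 names nonserious AEs leading to discontinuation for summary

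*SAP*

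**What the plan says.** Protocol 9.3 lists the safety information to be summarised with descriptive statistics: "The available information on all nonserious AEs leading to discontinuation, SAEs, and all other AEs". Nonserious AEs leading to discontinuation come first and are named separately from SAEs and from the remaining AEs.

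SAP 17.2.1 sets out four rows for the overall AE summary, by method of tissue collection, on the participants who had tissue sampled by impression cytology (IC) or superficial keratectomy (SK):

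- any procedure-related AE ("Participants with at least one AE related to the IC or SK procedure");
- any SAE related to study participation or to the procedure;
- "Participants with at least one SAE leading to study discontinuation";
- AE leading to death.

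Beyond the overview, "AEs and SAEs will be presented in tables by PT and sorted by decreasing frequencies on total, and broken down by maximum grade". The section closes with a listing: "All secondary safety data will also be included in a by-participant listing on the all-treated population".

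Two other protocol sections bear on the point. Section 7.1 says that a participant "may be withdrawn at any time at the discretion of the investigator for safety, behavioral, or compliance reasons", so withdrawal for safety does not depend on seriousness. Section 8.1.3 limits what is collected: "AEs related to the IC or SK procedure only will be collected from the start of intervention until the last follow-up visit".

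**The concern.** The safety profile of the IC or SK procedure is a secondary objective, and whether an AE made a participant leave is one of the plainer measures of tolerability. The protocol names two groups that could supply such events, nonserious AEs leading to discontinuation and SAEs. The SAP's discontinuation row keeps only the serious part and leaves out the part that the protocol ties to discontinuation by name.

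The omitted part matters for this procedure. The risks that Protocol 2.3 describes for SK are pain, infection, delayed healing and haze that is not visually significant. Many such events need not meet the seriousness criteria of Protocol 10.2.2, although some, such as a severe infectious keratitis, could. Someone scanning the overview might take a zero in the discontinuation row to mean that no AE led to withdrawal, when the row can show only that no SAE did.

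**Working it through.** There is no planned figure to reproduce. The study is descriptive, SAP 6.4 rules out tests, and the target of 5 in Protocol 9.2 is a qualitative judgement. The check is a comparison of texts followed by simple counts.

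**Step 1. Follow one case through the visible outputs.** Take a participant who has a nonserious procedure-related AE and withdraws because of it.

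| Output | Counts the AE? | Ties it to withdrawal? |
|---|---|---|
| Overview row: any procedure-related AE (SAP 17.2.1) | Yes | No |
| Overview row: related SAE | No | No |
| Overview row: SAE leading to study discontinuation | No | No |
| Overview row: AE leading to death | No | No |
| PT tables by maximum grade | Yes | No |
| By-participant safety listing | Yes | Not stated |
| Disposition (SAP 8.1, visible text) | Screening counts and screen failures only | Not visible; the rest is blacked out |

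The AE is captured. What is missing from every visible AE summary is its link to the withdrawal, and that link is what defines the category in Protocol 9.3.

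**Step 2. Is the change declared?** The visible text of SAP 3.3 explains only the added populations. A blacked-out block follows, so a declaration there can be neither confirmed nor excluded.

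**Step 3. Do the two documents mean the same discontinuation?** Protocol 9.3 does not say whether it means the study or the intervention. Each participant has one procedure, and Protocol 7.1 treats withdrawal as ending both intervention and study. Study discontinuation, the SAP's term, is therefore the natural reading.

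**Step 4. Size.** The documents give no withdrawal rate, so the number is an assumption. Let k participants withdraw because of a nonserious procedure-related AE and none because of an SAE.

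- Current SAP row: 0 for every k.
- Protocol category: k, with percentage 100 × k / N.

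| k (assumed) | N = 25 (maximum who complete the procedure, Protocol 4.1) | N = 5 (if only 5 have SK) |
|---|---|---|
| 1 | 1/25 = 4% | 1/5 = 20% |
| 2 | 2/25 = 8% | 2/5 = 40% |

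The denominator of 5 is also an assumption. Five is the target for evaluable SK samples, while the AE table includes participants whose specimen was not evaluable (SAP 5.3), so the SK column may hold more than 5.

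**The case against.** The strongest reply is that little is lost. The row is labelled as an SAE row, so a careful reader will not take it for all AEs. The same events count in the any-AE row, in the PT tables and in the listing, and with at most 25 participants a listing can be read in full. Protocol 7.1 expects few withdrawals. Delayed healing leads under the protocol to further follow-up until healing is confirmed, not to withdrawal. All of this stands, and it limits the importance of the point.

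The second reply is that the blacked-out text may answer it. SAP section 8 covers disposition and withdrawals, yet only one sentence of 8.1, on screening, can be read. The output templates, which SAP 7 says fix the content of the tables, are not among the documents. A summary of withdrawal reasons may exist there. This also stands: a reader might infer that these withdrawals appear in no summary at all, but the documents support only that they appear in no visible AE summary.

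The third reply is that Protocol 9.3 is a general description and prescribes no table layout. That is correct. It asks for a descriptive summary of the category, and neither an overview row, a split by seriousness nor a split by collection method is required by its text. The category itself is named, however, and the AE section of the SAP, whose list of overview rows is fully legible, does not deliver it.

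**Conclusion.** The mismatch is real but minor. SAP 17.2.1 narrows a safety category that Protocol 9.3 names, and no visible text explains why. The loss is the tabulated link between a nonserious procedure-related AE and withdrawal, not the AE itself. Under the assumption of one such withdrawal and none from an SAE, the row shows 0 where the protocol's category would show 1, which is 4% of 25 or 20% of 5. These are illustrations of scale, not estimates.

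Two stronger readings should be resisted. One is that withdrawals caused by AEs vanish from the report: only the one row necessarily reads zero for them, and the events remain in the any-AE row, the PT tables and the listing. The other is that corneal AEs in general are affected: only AEs related to IC or SK are collected, so corneal events due to belantamab mafodotin alone lie outside the AE data under both documents. The primary endpoint is untouched.

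The conclusion rests on the visible text. A withdrawal-reason table in SAP 8.1 could supply the summary, and a statement in SAP 3.3 could account for the change.

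**What to change.** In SAP 17.2.1, widen the discontinuation row to participants with at least one AE leading to study discontinuation, and show serious and nonserious separately within the existing table by collection method. The split keeps the current SAE count and adds the protocol's category; this layout is a recommendation, not something Protocol 9.3 dictates. If the blacked-out part of SAP 8.1 already tabulates AE-related withdrawals, a cross-reference from 17.2.1 would do. If the omission is intended, declare it in SAP 3.3.

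First confirm that the eCRF links nonserious AEs to discontinuation. The SAE row implies such a link for serious events, but the eCRF is not among the documents. If the field exists, the cost is a change to one row and its wording. If it does not, the link would have to be made from the recorded reason for withdrawal, if there is one, which is manageable with at most 25 participants.

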5.2. ALL-TREATED POPULATION

All-treated population is defined as all participants screened who are enrolled (without screen failure).

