5.3. IMPRESSION CYTOLOGY OR SUPERFICIAL KERATECTOMY PROCEDURE (ICSK) POPULATION

IC or SK (ICSK) population is defined as participants from all-treated population who had a tissue sample collected using Impression Cytology (IC) or Superficial Keratectomy (SK) procedure, whether or not the specimen is evaluable.

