9. DEMOGRAPHIC CHARACTERISTICS

Demographic characteristics will be presented on the all-treated population.

The following demographic data will be reported for this study:

- Age (years) - calculated relative to year of consent
- Sex
- Ethnicity
- Race
- GSK2857916 parent study or patients on commercial prescriptions

Demographic characteristics will be presented in a table by method of tissue collection (impression

Document: \\ieedc-vnasc01\Biosdata\GSKGSK2857916\UZA78766\Biostatistics\Documentation\SAP\UZA78766_214098_SAP_v2.0_12OCT2022.docx

Author: PPD

Version Number: 2.0

Version Date: 12OCT2022

Template No.: CS_TP_BS016 Revision 6

Reference: CS_WI_BS005

Effective Date: 02Dec2019

cytology/superficial keratectomy/not collected).

Demographic characteristics will also be included in a by-participant listing.

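### SAP 17.2.1 sources AEs leading to death only from the parent study's eCRF, so the death row and death listing cannot capture a fatal event recorded only in this study (minor; wrong as written)

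*SAP*

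**What the plan says.** SAP 17.2.1 plans an overall safety summary on the ICSK population, which "will be provided by method of tissue collection (impression cytology/superficial keratectomy) summarizing" four counts. The second is "Participants with at least one SAE related to the study participation or to the IC or SK procedure"; the fourth counts participants with an AE leading to death. The source for that fourth row is then fixed: "AEs leading to Death are those events which are recorded on the Adverse Events page of the parent study eCRF". To qualify, an event must meet at least one of four criteria: the term reported, the outcome, the seriousness category, or CTCAE Grade 5.

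The same definition feeds a listing: "AEs leading to death will be presented in a by-participant listing on the all-treated population". Separately, "All secondary safety data will also be included in a by-participant listing on the all-treated population".

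On who is in the study, SAP 9 records drug source as "GSK2857916 parent study or patients on commercial prescriptions". SAP 1 and protocol 4.1 also treat trial participation and prescription as alternative routes in. The ICSK population is defined without reference to drug source, as "participants from all-treated population who had a tissue sample collected using Impression Cytology (IC) or Superficial Keratectomy (SK) procedure". The all-treated population (SAP 5.2) is likewise defined by enrolment alone.

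**The concern.** The definition points to another trial's database. Some participants have no record in any such database, and this study collects the relevant events itself. A participant treated only on prescription counts in the ICSK denominator but, read literally, could never count in the death row.

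At stake is consistency on the most serious outcome within a secondary objective, the safety profile of the procedure. A zero in the death row should mean that no fatal event was recorded in this study. Under the stated source rule it does not show that, and a fatal event that did occur could appear in other safety outputs while the outputs dedicated to deaths stayed empty.

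**Working it through.** The plan gives no figure to reproduce here. The check is to read the definition as a selection rule and follow an event through it.

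**1. Is the parent study the same as this study?** No. SAP 9 sets the parent study against commercial prescription, and SAP 1 speaks of another GSK trial. Where the SAP draws on this study's own pages (sections 16, 17.1 and 17.2.2), it names the eCRF page without the parent-study qualifier.

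**2. Does this study capture fatal events itself?** Yes. Protocol 10.1.6 provides for its own CRF or eCRF. Protocol 8.1.3 collects AEs and SAEs related to the procedure, and SAEs related to study participation from consent onward. Protocol 8.1.7 requires a Death section of the CRF for every death.

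**3. Does any visible text bring those records into the death outputs?** None was found. Part of SAP 8.1 is redacted, and the output templates mentioned in SAP 7 are not available.

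**4. Apply the rule to each case.**

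| Where the fatal event is recorded | Death listing (all-treated) | Death row (ICSK) |
|---|---|---|
| Parent study AE page | Enters | Enters if the participant is in ICSK |
| Only this study's eCRF, participant from a trial | Does not enter | Does not enter |
| Only this study's eCRF, prescription patient never in a parent trial | Does not enter | Does not enter |

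The second case is possible because participants need not be on active treatment when they join (protocol 4.1, SAP 3.1). A prescription patient who was earlier in a parent trial, and whose event is also recorded there, falls in the first case.

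**5. Where would a missed event still be seen?** For an ICSK participant with a fatal procedure-related SAE: the related-AE row, the related-SAE row, the preferred-term tables by maximum grade, and the general safety listing. For an enrolled participant outside ICSK with a fatal SAE related to study participation: the general safety listing only.

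**6. Size in counts.** Let D be the number of ICSK participants with a fatal event within this study's collection scope, and k the number of those whose event is recorded only in this study's eCRF. The literal rule finds D − k of them, a shortfall of D − (D − k) = k. With k = 0 nothing changes; with k = 1 the row is one short. The documents do not give k or the number of prescription patients. k is most likely 0, since the risks the protocol describes for SK (pain, infection, delayed healing, haze, worsening vision) are ocular.

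**The case against.** The strongest reply is that the source may be deliberate. The first two rows of the summary carry a relatedness qualifier and the death row carries none. Because this study collects only related events, going to the parent study could be a way to count deaths from any cause. The documents neither confirm nor exclude this, so it stands as an open question about scope. It does not rescue the sentence. An all-cause count taken from the parent study would still omit prescription patients without one, and this study's own Death CRF section already covers all deaths.

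A second reply is that the wording is a leftover. The protocol's summary of changes says companion-study language was removed once prescription patients were admitted. That is plausible, but this SAP states that it is based on amendment 02 and itself names prescription patients, so its current text still needs correcting.

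A third reply is that the study is exploratory and descriptive, the primary endpoint is untouched, and the templates may already handle the matter. This stands as a limit on severity and on any claim about what the tables will show.

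Three stronger readings are tempting and not supported:

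- A reader might infer that deaths would vanish from the report. They would not: the general safety listing, and for ICSK participants the related-event and graded tables, do not use this definition.
- A reader might infer that unrelated parent-study deaths will inflate the row. The four criteria set no relatedness or time limit, but no visible text says that parent-study data will be merged.
- A reader might infer that the row was meant for procedure-related deaths only. The SAP does not say so.

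**Conclusion.** The point holds as a minor defect: a stated selection rule that names the wrong source for this study. It affects one table row and one listing. It has no bearing on the primary endpoint, the sample size or any error rate, and no percentage effect can be given.

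The conclusion rests on two assumptions. First, the single named source is taken as exclusive, because nothing visible adds another. Second, the outputs are taken to be programmed as the text reads, which cannot be checked without the templates. Given both, any contradiction between outputs arises only if a fatal event is recorded solely in this study's eCRF, and that is unlikely.

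**What to change.** In SAP 17.2.1, replace the reference to the parent study's eCRF with this study's (214098) eCRF, applied to all participants whatever their source of belantamab mafodotin. Keep the four criteria.

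Then:

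- Footnote the death row and the death listing to say that this study collects AEs and SAEs only if they are related to the procedure or, for SAEs, to study participation.
- List any other deaths from this study's Death CRF section (protocol 8.1.7) separately, by participant.
- Check the AE/SAE records and the Death section against each other before database lock.
- If an all-cause count from the parent study was intended, make it a separate, labelled output that states that prescription patients without a parent study are not covered.

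The cost is one SAP sentence, matching footnotes, one short listing and one reconciliation check. The main change uses data the protocol already requires; only the optional parent-study output would need data from elsewhere.
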